6. DATA HANDLING CONVENTIONS

6.1. DATA HANDLING CONVENTIONS FOR SITE QUESTIONNAIRE

Not applicable.

6.2. DATA HANDLING CONVENTIONS FOR PATIENT DATA OUTLIERS

Any outlier identified prior to database lock which is impossible/implausible will be excluded from the analysis. A search of outliers should be performed before the database lock and actions with the sponsor should be defined.

6.3. DATA HANDLING CONVENTIONS FOR PATIENT REPORTED OUTCOMES

The management of missing data for PRO is described in [Appendix A](#).

6.4. MISSING DATA

For the primary endpoint, in case of treatment discontinuation due to lack of efficacy (as defined in Protocol Version 2 section 11.4.2.1) or adverse event (except for AEs due to NSAID), the last available endpoint before the considered event will be taken in account (for [RAID](#) score for primary endpoint and for all other secondary endpoints). For all other cases, missing data will not be replaced.

MISSING OR INCOMPLETE DATES

For all dates (except adverse events and concomitant treatments):

- If only day is missing, it will be replaced by '15'
- If day and month are missing, day will be replaced by 1 and month will be replaced by July '7'
- In case of missing year or complete missing date, no replacement will be performed

For dates relative to adverse events (AE) and concomitant treatments, if a date is completely or partially missing, date will not be replaced but:

- If day is missing and start date/end date of AE/treatment occurred before or the same month as the end of study, AE/treatment will be considered as "treatment-emergent" by default.
- If day and month are missing and start date/end date of AE/treatment occurred the same year as the end of study, AE/treatment will be considered as "treatment-emergent" by default.
- In case of missing year or complete missing date, start date/end date of AE/treatment will be considered as "treatment-emergent" by default.

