
STATISTICAL CONSIDERATIONS
	
Sample size determination:
 
According to the literature and previous studies having assessed sarilumab, the standard deviation (SD) of the RAID score could be estimated at 2.5 points. On this basis, a sample size of 140 included patients in order to have at least 112 evaluable patients (assuming almost 20% of non-evaluable patients), produces a precision, two-sided 95% confidence interval (CI), with a distance from the mean to the limits that will be less than 0.5 (considering 20% non-evaluable patients) when the estimated SD is 2.5, assuming that the change from baseline will be from 30% to 50% of baseline score.
 
Analysis populations:
 
 
• Intent-to-treat (ITT) population: all patients who met the eligibility criteria and who are actually treated.
 
• Safety population: all patients who have signed the Informed Consent Form (ICF) and have been exposed to at least one dose or part of a dose of IMP.
 
• Per-protocol population: patients of ITT population without major protocol deviations.
 
 
Primary analysis:
 
The primary study objective is to assess the change in RAID score from baseline to W24.
 
The number of available data, mean, standard deviation, median and range (minimum, maximum) will be provided with the 95% confidence interval of the mean change from baseline to W24. Main analysis will be performed on ITT population. Sensitivity analysis will be conducted in reproducing the same analysis using the per-protocol population.
 
In addition, multivariate analyses such as ANCOVA, Logistic Regressions and Multiple Correspondences analysis can be performed from baseline in order to exploratory explain patient profiles.
 
Analysis of secondary endpoints:
 
All secondary parameters will be described; 95% CI will be provided.

DURATION OF STUDY PERIOD (per patient)	The total duration of the core study period per patient is expected to be approximately 32 weeks: 

• Up to 4-week screening

• 24 weeks treatment

• 2-4 week post-treatment observations.

 For patients who will enter in the LTE period, a maximum of another 24 weeks is planned.
---	--

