## 11 STATISTICAL CONSIDERATIONS

### 11.1 DETERMINATION OF SAMPLE SIZE

The primary study objective is to assess the change in RAID score from baseline to W24. A sufficient precision (half-length of the 95% confidence interval) is required. According to the literature (44, 45, 46) and findings from the MONARCH and TARGET studies (22, 33), the standard deviation (SD) of the RAID score could be estimated at 2.5 points. On this basis, a sample size of 140 patients (122 evaluable, if 20% non-evaluable patients) produces a precision, two-sided 95% confidence interval (CI), with a distance from the mean to the limits that will be less than 0.5 when the estimated SD is 2.5. Table below gives the 95% CI of change from baseline to W24 of RAID score with this precision (0.44), assuming that the change from baseline will be from 30% to 50% (MCII defined by Dougados in 2012; 47) of baseline score.

Expected change from baseline to W24 of RAID score (Relative to baseline %)	RAID score at Baseline	Expected change from baseline to W24 of RAID score (Absolute value)	95% CI (precision =0.5)
30%	65	2,0	[1,5 ; 2,5]
	5	1,5	[1,0 ; 2,0]
	3,5	1,1	[0,6 ; 1,6]
50%	6,5	3,3	[2,8 ; 3,8]
	5	2,5	[2,0 ; 3,0]
	3,5	1,8	[1,3 ; 2,3]

*Note that on MONARCH study (22), the % of change from baseline was 49.6% (3.32/6/69) and in TARGET study (33) 47.4% (3.24/6.83).*

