1.4. DETERMINATION OF SAMPLE SIZE

The primary study objective is to assess the change in **RAID** score from baseline to W24. A sufficient precision (half-length of the 95% confidence interval (CI)) is required. According to the literature [\[1,2,3\]](#) and findings from the MONARCH and TARGET studies [\[4,5\]](#), the standard deviation (SD) of the **RAID** score could be estimated at 2.5 points. On this basis, a sample size of 140 patients (122 evaluable, if 20% non-evaluable patients) produces a precision, two-sided 95% confidence interval (CI), with a distance from the mean to the limits that will be less than 0.5 when the estimated SD is 2.5. Table below gives the 95% CI of change from baseline to W24 of **RAID** score with this precision (0.44), assuming that the change from baseline will be from 30% to 50% (MCII defined by Dougados [\[6\]](#) in 2012) of baseline score.

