1.6. MODIFICATIONS FROM THE PROTOCOL

Analysis sets definition have been reviewed:

Population	Protocol definition	Statistical analysis plan definition
Enrolled patients	No definition	All patients screened, who have signed the Informed Consent Form (ICF) and who never took the study treatment at any time before baseline.
Intent-to-treat (ITT) population	All patients who met all the eligibility criteria and who are actually treated.	All patients included (i.e. for whom the inclusion decision "Has the decision to include the patient been taken" is 'Yes') and who took the treatment at least once
Per-protocol population	Patients of ITT population without major protocol deviations. Major deviations will be defined in the statistical analyses plan before database frozen.	Patients of ITT population without major protocol deviations as defined during the Data Review meeting and who are evaluable for the main criterion

Data will be presented according to a subgroup not defined in the protocol. This subgroup has 3 categories^{DD}:

- Patients treated with csDMARDs for whom Sarilumab is prescribed in addition to csDMARDs at baseline.
- Patients treated with biological therapy for whom Sarilumab is prescribed in addition to csDMARDs at baseline.
- Patients previously treated with csDMARDs or biological therapy for whom only Sarilumab in monotherapy is prescribed at baseline.

Also, an analysis has been performed with all screened patients who have met all the eligibility criteria and who have received the treatment at baseline visit (D1). Only data from the baseline visit have been analysed.

In the protocol section 11.4.1.3, compliance should be evaluated according to the planned dose required by the protocol. No planned dose is required by the protocol. Hence, compliance will be evaluated according to the number of injections during the study (see section 5.1.4).

Adverse events will not be described by SOC, HLG, HLT and PT but only by SOC and PT.

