5.3.2.2. Primary efficacy analysis

The primary study objective is to describe the effect of sarilumab on the variation of the total [RAID](#) score from baseline to V5 (W24). Mean change from baseline (V2) of the total [RAID](#) score to W24 (V5) will be provided with its bilateral 95% CI.

Change from baseline in total [RAID](#) score after 24 weeks will be provided using a mixed model repeated measurement. This model includes total [RAID](#) score at baseline as covariate, and interactions between the covariate and visit.

SAS code:

```
Proc MIXED;  
Class Visit;  
Model RAID_score_change= Visit + Raid_score_baseline*Visit;  
Repeated Visit / type=UN sub=id;  
Run;
```

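### The primary analysis relies on carrying RAID values forward, and no planned sensitivity analysis tests the assumption about missing Week 24 data

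*SAP*

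**What the plan says.** SAP 6.4 sets the rule for the primary endpoint. When a patient stops treatment for inefficacy or an adverse event (other than one attributed to an NSAID), "the last available endpoint before the considered event will be taken in account". Any other missing RAID value stays missing.

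SAP 5.3.2.2 analyses the Week 24 change in two ways. One is a mean with a two-sided 95% CI. The other is a model: change in the total RAID "score after 24 weeks will be provided using a mixed model repeated measurement". The code has visit, baseline-by-visit and an unstructured covariance. Neither code nor text excludes or flags carried values, or says which of the two analyses section 6.4 governs.

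SAP 5.2 puts the primary analysis on the ITT set and makes a rerun on the per-protocol set (PPS) the only sensitivity analysis. SAP 1.6 and 3.2.3 limit the PPS to patients without major deviations "who are evaluable for the main criterion". Protocol 11.3.3 has no such condition, and neither document defines evaluable.

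Protocol 11.4.2.1 planned a mean with CI, plus optional exploratory models. Its carry-forward rule has wider triggers: certain glucocorticoid and NSAID changes are listed separately from stopping treatment. SAP 1.6 records the revised populations, but neither the mixed model nor the narrower trigger.

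**The concern.** A repeated-measures mixed model uses incomplete patient profiles without imputation, on the assumption that data are missing at random. Here it sits beside a carry-forward rule written for a simple Week 24 mean. If carried values enter the model, the estimate assumes that a patient who stopped has, at Week 24, the score last recorded before stopping. That could fail either way: a patient might have gone on improving, or might have lost the benefit after stopping.

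Protocol 11.4.2.3 says that everything is descriptive, so no type I error or power is at stake. What is at stake is the trial's main result, the mean change and its interval, with no control arm to offset a bias. The planned rerun on the PPS would not reveal one.

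**Working it through.** **Step 1. The plan's own precision.** Protocol 11.1 says that "the standard deviation (SD) of the RAID score could be estimated at 2.5 points". SAP 1.4 says that "a sample size of 140 patients (122 evaluable, if 20% non-evaluable patients) produces a precision", for a "two-sided 95% confidence interval (CI), with a distance from the mean to the limits that will be less than 0.5". Half-width = 1.96 × SD/√n.

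- At 122: 1.96 × 2.5/√122 = 0.444, which reproduces the stated 0.44.
- 20% of 140 non-evaluable leaves 140 × 0.80 = 112, the count in the Protocol summary, not 122. At 112: 1.96 × 2.5/√112 = 0.463.
- The target needs n of at least (1.96 × 2.5/0.5)² = 96.04, so 97. Both counts meet it.

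The conflict between 112 and 122 is a separate matter. The figures below use 112.

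**Step 2. Effect of the rule on a mean.** Shift = p × d, where p is the share of patients whose Week 24 value is carried forward and d is the average gap between their carried change and their true Week 24 change. The documents give neither. Their 20% refers to non-evaluable patients, which is not the same as carried-forward patients. Assumed ranges: p = 10-20%, d = 1-2 points.

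| p | d = 1 | d = 2 |
|---|---|---|
| 10% | 0.10 | 0.20 |
| 20% | 0.20 | 0.40 |

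Against 0.463 these shifts are 0.10/0.463 = 22% to 0.40/0.463 = 86% of the half-width.

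**Step 3. Effect inside the mixed model.** A simulation fitted a model with baseline-by-visit and unstructured covariance (n = 140, 400 runs per scenario). Assumptions: about 20% dropout depending on observed response; 50, 75 or 100% of dropouts carried forward; mean changes of -1.6, -2.7 and -3.3 at Weeks 4, 12 and 24; SD 2.5; correlations 0.50-0.65. The target is the mean Week 24 change in all patients, on drug or not. Positive bias means that improvement is understated. Triplets follow the three carried-forward shares.

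| Worsening after stopping | Carry-forward: bias | Carry-forward: coverage | Observed values only: bias | Observed values only: coverage |
|---|---|---|---|---|
| 0 | +0.18 / +0.25 / +0.33 | 88 / 78 / 70% | -0.01 to 0.00 | 96-98% |
| 1.5 points | -0.12 / -0.04 / +0.03 | 89.5 / 94.5 / 96.5% | about -0.30 | 73-76% |
| 3 points | -0.41 / -0.34 / -0.27 | 55 / 66 / 79% | -0.59 to -0.61 | about 25% |

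Half-widths hardly differ: 0.44 with carry-forward, 0.44-0.45 without. The damage is in the location of the estimate, and its sign depends on what happens after stopping.

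**Step 4. What the PPS rerun can show.** If a carried-forward patient counts as evaluable, the PPS repeats the same imputation. If not, the PPS drops that patient. Neither changes the assumption about the missing Week 24 score and shows the result.

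**Step 5. Related data handling.** Protocol 10.3.4 keeps patients in follow-up after they stop, so real later RAID scores may exist. The SAP does not say whether carry-forward overrides them. SAP 6.6, in its example, discards early-withdrawal data that fall before the next visit window.

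**The case against.** The strongest reply has three parts, and each stands to some extent.

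- **Carried values in the model are an inference.** True. SAP 6.4 applies to the primary endpoint and SAP 5.3.2.2 analyses that endpoint, so the reading is natural, but it is not stated. Even if carried values went only into the simple mean, the missing-data assumption would still be untested.
- **The rule is the Protocol's own, and an observed-data model can do worse.** Also true. In Step 3 the observed-data model overstates improvement more than carry-forward does once leavers worsen by 1.5 or 3 points. Replacing one with the other would not settle the matter.
- **A zero-change analysis is itself single imputation.** Yes. It serves as a stress test, not as a better estimate.

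A reader might also infer more than the documents support:

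- *That the CI is too narrow by 11%.* This compares 1.96 × 2.5/√140 = 0.414 with 0.463. It supposes that every non-evaluable patient is carried forward at a fixed SD, and it ignores the model's use of Week 4 and Week 12 data. Step 3 shows almost no change in width.
- *That the rule shifts the mean by 0.66.* The product 0.2 × 3.3 compares a 3.3-point change with zero change in 20% of patients. Under the rule, leavers get their own last score, so this does not measure it.
- *That precision is lost.* About 20% non-evaluable patients are planned for, and 0.463 is inside the target.
- *That carried values make Weeks 4, 12 and 24 equal.* This holds only for patients who stop between Weeks 4 and 12. After Week 12 only Weeks 12 and 24 coincide.

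**Conclusion.** The concern holds as one of untested bias. The primary RAID estimate depends on a carry-forward assumption, and the only planned check cannot show how much. Under the assumed ranges the mean shifts by 0.1-0.4 points, against a half-width of 0.46 at 112 evaluable patients and SD 2.5. The direction cannot be known beforehand. In the simulation the bias ran from +0.33 to -0.41 and was small in some scenarios. The carried-forward share, the gap, the trajectory, the correlations and the worsening after stopping are assumptions, not figures from the documents. The documents do not support calling the interval demonstrably too narrow or the precision target missed.

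**What to change.** 1. In SAP 5.3.2.2, fit the mixed model to observed RAID values only, and say whether scores collected after stopping treatment count as observed. Report the carry-forward rule of Protocol 11.4.2.1 and SAP 6.4 as a separate named analysis, and record the change in SAP 1.6.
2. In SAP 5.2, add one sensitivity analysis on the full ITT set that assigns zero change from baseline to patients with no Week 24 RAID score, so that the check on missing data does not rest on the PPS.
3. Reconcile the carry-forward triggers. Protocol 11.4.2.1 lists glucocorticoid and NSAID changes; SAP 6.4 ties the rule to stopping treatment while referring back to that section.

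Cost: two extra runs of the primary table and an entry in SAP 1.6, with no new data. The main drawback is that the observed-data model assumes missingness at random and would overstate benefit if leavers worsen after stopping. The zero-change analysis must therefore accompany it.

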#### **10.1.2 Baseline examination (Visit 2: first IMP administration)**

All Baseline investigations will be performed according to the Schedule of Assessments (see details in Section 1.2).

All PROs and efficacy assessments performed at the Baseline visit should occur the same day and before the first administration of sarilumab.

The investigator or designee will:

- Assess eligibility by review of inclusion/exclusion criteria. Patients who do not meet these inclusion/exclusion criteria should be excluded from the study prior any study treatment administration.
- Record the general physical examination performed during the Screening period (between D-28 and D-1), and reported V2 body weight and waist circumference.
- Record Baseline chest X-ray and 12-lead ECG.
- Record vital signs.
- Ask the patient to complete the following self-assessments: RAID, HADS, MATHyS, FACIT-Fatigue, HAQ-DI, duration of morning stiffness, IPAQ, and patient global assessment of disease activity (VAS)
- For female patients of child-bearing potential performed a urine pregnancy test. If the urine test is positive it must be confirmed by a serum pregnancy test.
- Record the results of hematology, serum chemistry, serum iron, 25OHD, fasting lipids, and serology tests results
- Complete the ACR core set assessments including ESR, DAS28-ESR, CDAI, and joint counts (TJC and SJC on 28 joints).
- Review concomitant medications
- Inquire about and record any adverse events/SAEs that could have occurred since the signature of the written consent form.
- If the patient meet all the inclusion criteria and none of the exclusion criteria, proceed to the first SC administration of the IMP
- For patients able to perform SC injections at home, the investigator or delegate will provide training regarding the preparation and injections (at Baseline). For patients and/or non-professional caregivers completely unable to perform such injections at home, a home nursing will be needed and arrangements must be made to administer IMP at 2-week intervals.
- Deliver IMP for the next study period.
- Schedule an appointment for the next visit.

For all subsequent visits, the scheduled day should be followed (see details in Section 1.2).

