#### **10.4.3 General guidelines for reporting adverse events**

- All AEs, regardless of seriousness or relationship to IMP, spanning from the signature of the informed consent form until the end of the study as defined by the protocol for that patient, are to be recorded on the corresponding page(s) or screen(s) of the eCRF.

- Whenever possible, diagnosis or single syndrome should be reported instead of symptoms. The Investigator should specify the date of onset, intensity, action taken with respect to IMP, corrective treatment/therapy given, additional investigations performed, outcome, and his/her opinion as to whether there is a reasonable possibility that the AE was caused by the IMP or by the study procedure(s).
- The Investigator should take appropriate measures to follow all AEs until clinical recovery is complete and laboratory results have returned to normal, or until progression has been stabilized, or until death, in order to ensure the safety of the patients. This may imply that observations will continue beyond the last planned visit per protocol, and that additional investigations may be requested by the monitoring team up to as noticed by the Sponsor.
- When treatment is prematurely discontinued, the patient's observations will continue until the end of the study as defined by the protocol for that patient.
- Laboratory, vital signs or ECG abnormalities are to be recorded as AEs only if:
  - Symptomatic and/or
  - Requiring either corrective treatment or consultation, and/or
  - Leading to IMP discontinuation or modification of dosing, and/or
  - Fulfilling a seriousness criterion, and/or
  - Defined as an AESI.

Instructions for AE reporting are summarized in Table 1.

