5.3.2.4. Safety analyses

All AEs (Serious AE (SAE), AE of special interest (AESI), Treatment-Emergent AE (TEAE), AE leading to death, TEAE leading to death) will be presented by System Organ Class (SOC) sorted by internationally agreed order¹ and Preferred Term (PT). A TEAE is defined as an AE occurring in the time from the first injection of IMP up to 14 days after the last injection. In case of AE/TEAE leading to death, cause of death will be provided.

Laboratory safety variables, vital signs and ECG values will be presented at each assessment.

A frequency table of the number and percentage of subjects will be provided for prior and concomitant therapies by therapeutic class (ATC). The table will be sorted by decreasing frequency of anatomic category followed by all other therapeutic classes. In case of equal frequency regarding anatomic categories, alphabetical order will be used.

The following definitions will be applied to laboratory parameters and vital signs

- The potentially clinically significant abnormality (PCSA) values are defined as abnormal values considered medically important by the Sponsor according to predefined criteria/thresholds based on literature review and defined by the Sponsor for clinical laboratory tests, vital signs (PCSA list provided in [Appendix J](#)).
- PCSA criteria will determine which patients had at least 1 PCSA during the on-treatment period, taking into account all evaluations performed during the on-treatment period, including unscheduled or repeated evaluations. The number of all such patients will be the numerator for the on-treatment PCSA percentage.

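### The SAP's partial-date rule for adverse events ignores first and last injection, so some AEs known from their month to be off treatment count as treatment-emergent, and some year-only dates are left unclassified

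*SAP*

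**What the plan says.** SAP 6.4 treats incomplete AE and concomitant-treatment dates apart from all others: "if a date is completely or partially missing, date will not be replaced but" three defaults apply.

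- Day missing: "If day is missing and start date/end date of AE/treatment occurred before or the same month as the end of study", the record is treatment-emergent.
- Day and month missing: "If day and month are missing and start date/end date of AE/treatment occurred the same year as the end of study", the record is treatment-emergent.
- Year or whole date missing: "In case of missing year or complete missing date, start date/end date of AE/treatment will be considered as" treatment-emergent, with no condition.

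The definition these defaults should serve is in SAP 5.3.2.4: "A TEAE is defined as an AE occurring in the time from the first injection of IMP up to 14 days after the last injection".

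AEs are collected before dosing. Protocol 10.4.3 has them recorded over a period "spanning from the signature of the informed consent form until the end of the study as defined by the protocol for that patient", and at the baseline visit (Protocol 10.1.2) the investigator must "record any adverse events/SAEs that could have occurred since the signature of the written consent form" ahead of the first injection. Screening lasts up to 28 days (SAP 1.1).

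**The concern.** A default that calls an AE treatment-emergent is sound when its timing is unknown. Here it also applies when the known month settles the timing. The day-missing bullet expressly takes in months earlier than the end-of-study month and sets no floor. No bullet mentions first injection, baseline or last injection, and neither document supplies a bound elsewhere. Because the date is not replaced, there is no imputed date to compare with Day 1 either.

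The study is single-arm, so the absolute TEAE counts are the safety result and no control arm offsets an over-count. SAP 5.3.2.4 tabulates TEAEs and TEAEs leading to death. A programmer following SAP 6.4 and one following SAP 5.3.2.4 would produce different counts from the same records.

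**Working it through.** The plan gives no figure to reproduce. The check applies the three bullets literally and compares each result with the earliest and latest dates that the partial date allows.

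**Illustrative patients (dates are assumptions).** Last injection is 22 weeks (154 days) after the first; end of study is 28 days after that.

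- Patient A: first injection 10 Apr 2018, last 11 Sep 2018, window closes 25 Sep 2018 (last + 14 days), end of study 9 Oct 2018.
- Patient B: first injection 10 Oct 2018, last 13 Mar 2019, window closes 27 Mar 2019, end of study 10 Apr 2019.

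| Patient | Recorded onset | SAP 6.4 result | Against the SAP 5.3.2.4 window |
|---|---|---|---|
| A | Mar 2018 | treatment-emergent | wholly before: wrong |
| A | Apr 2018 | treatment-emergent | could be either: reasonable |
| A | Oct 2018 | treatment-emergent | wholly after: wrong |
| A | 2018 only | treatment-emergent | could be either: reasonable |
| A | none | treatment-emergent | unknown: reasonable |
| B | Sep 2018 | treatment-emergent | wholly before: wrong |
| B | Apr 2019 | treatment-emergent | wholly after: wrong |
| B | 2018 only | no bullet applies | could be either: left unclassified |

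**Lower bound: what share is provable?** Let screening last S days (S at most 28), with onsets spread evenly over it and Day 1 equally likely on any date of a 365-day year. If Day 1 is day d of its month, the pre-dose days falling in the previous month number S − d + 1 when d ≤ S, and none otherwise. Summing over d gives S(S + 1)/2 per month. Over 12 months, divided by 365 × S days:

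share = 6(S + 1)/365

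- S = 7: 48/365 = 13%
- S = 14: 90/365 = 25%
- S = 28: 174/365 = 48%

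These are shares of screening AEs with a missing day, not of all AEs.

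**Upper bound.** For patients who complete, the last visit is 2 to 4 weeks after the last injection (Protocol 6.2.2), so the mismatch is at most 28 − 14 = 14 days. It yields a provable error only if a calendar month begins in that gap. The October 2018 and April 2019 rows depend on this: with the last injection at Week 24 instead, patient A's window would close on 9 Oct 2018 and October would be ambiguous.

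The exposure is larger for patients who stop early, because Protocol 10.3.4 and 10.4.3 keep them under observation to the planned end of study. Suppose patient A had the last injection on 8 May 2018 (Day 1 + 28 days) and was followed to Week 24, 25 Sep 2018 (Day 1 + 168 days). The window closes on 22 May. Day-missing onsets in June, July, August or September are all wholly after it, yet all are classed treatment-emergent.

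**Year-only gap.** For patient B, AE recording could start no earlier than 12 Sep 2018 (Day 1 − 28 days). An AE dated only 2018 therefore began between 12 Sep and 9 Oct (28 days, before treatment) or between 10 Oct and 31 Dec (22 + 30 + 31 = 83 days, on treatment). Most of that range is on treatment, yet no bullet classifies the event.

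**The case against.** The strongest reply is that the default is deliberately conservative and the consequence small. The analysis is descriptive without tests (Protocol 11.4.2.3), all AEs are tabulated as well as TEAEs, and the main error over-counts rather than hides events. Onset date is a required item (Protocol 10.4.3) and queries run through the eCRF (Protocol 13.4), so few dates may stay incomplete. All of this stands and keeps the point minor. It does not defend a default applied where the month already rules out the treatment window, and the year-only gap is not conservative.

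It can also be argued that a default yields to other information. The text states no such exception, and its condition names earlier months outright.

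Two stronger readings are tempting but not supported:

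- A reader might infer that every screening AE with a missing day is misclassified. An onset in the same calendar month as the first injection cannot be placed before or after dosing, and treatment-emergent is the proper default for it.
- A reader might infer that every past drug known only by month and year would be reported as taken on treatment. Protocol 8.8 limits concomitant therapy to medicines used from 7 days before Screening. SAP 5.1.1 presents RA medication history separately, as ongoing or ended at baseline, so older drugs may fall under SAP 6.4's rule for other dates, where a missing day becomes 15. The SAP does not settle which rule applies. The safety table by ATC class in SAP 5.3.2.4 pools prior and concomitant therapies, and treatment-emergent is not defined for medicines. The medication effect is confined to prior or concomitant labelling.

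**Conclusion.** The concern holds for AEs, in both directions. SAP 6.4 contradicts the TEAE window in SAP 5.3.2.4 by counting day-missing events whose month is wholly before the month of first injection, or wholly later than 14 days after the last injection. It also leaves unclassified some year-only events that may be on treatment, when treatment spans two calendar years.

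The provable pre-dose error affects about 13% to 48% of day-missing screening AEs for 7- to 28-day screening, given evenly spread onsets and start dates. The number of such AEs is not given, so no change in the TEAE count can be stated. The post-treatment error falls mainly on patients who stop early and stay in follow-up; its size depends on how many do so and how long they are followed. This is a minor correction.

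**What to change.** **AEs.** Replace the three bullets with one test tied to SAP 5.3.2.4. An incomplete onset date is treatment-emergent unless:

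- its known month or year lies wholly before first injection;
- its known month or year lies wholly after last injection plus 14 days; or
- a known end date precedes first injection.

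Apply this to year-only dates in any year. Dates with the year missing keep the default unless a known end date precedes first injection. In the examples above, March 2018 and October 2018 (patient A) and September 2018 and April 2019 (patient B) leave the TEAE set. April 2018, 2018 only and the missing date stay in it for patient A, and 2018 only becomes treatment-emergent for patient B.

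**Medicines.** Do not reuse the onset test: applied to start dates, it would drop ongoing background csDMARDs, which must be stable for at least 4 weeks before Baseline (Protocol 7.1) and are expected to continue (Protocol 8.8.2). Classify a medicine as prior only if the known part of its stop date lies wholly before first injection. Ongoing medicines, and those with an unknown stop date, remain concomitant whatever their start date. State also whether RA medication history follows this rule or the rule for other dates.

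The cost is one paragraph of SAP text and one derivation. No new data are needed.
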